22.3.2 Part III - Schedule of Events

Evaluation	In clinical unit (Days)												Follow-up EOS/ET (± 3 days)			
	-1	1	2	3	4	5	6	7	8	9	10	11	12	13	14	21
Discharge from Clinical Unit															X^1	
Run-In Assessment ²	X															
SUBOXONE SL film ³ Administration		X	X	X	X	X	X	X	X	X						
INDV-2000 Administration				X	X	X	X	X	X	X	X	X	X	X		
PK Sampling ⁴			X	X						X	X			X	X	
Physical Examination ⁵	X		X			X				X		X			X	X
Urine Drug Screen	X							X							X	X
Alcohol test	X							X							X	
Urine Pregnancy Test	X														X	X
Urinalysis	X							X							X	X
Clinical Laboratory Assessments (Chemistry and Haematology) ⁶	X			X		X				X		X			X	X
Vital Signs ⁷	X	X	X	X		X		X		X		X		X		X
12-Lead Electrocardiogram ⁸	X	X	X	X		X		X		X		X		X		X

C-SSRS ¹³	X		X		X		X		X		X		X		X	X
AE Assessment	X	X	X	X	X	X	X	X	X	X	X	X	X	X		X
Concomitant Medication	X	X	X	X	X	X	X	X	X	X	X	X	X	X		X

- 1: Discharge occurs the morning of Day 14 and the clinical facility will provide the subject with options for their continued treatment for OUD.
- 2: Subjects must meet Run-In assessment criteria (defined in Section 5.4) on Day -1 prior to completing subsequent Day -1 procedures within this table.
- 3: Dose after INDV-2000 AM dose.
- 4: For PK collection timepoints, refer to Section 22.5, Appendix 5 Plasma PK Sampling Windows.
- 5: A full physical examination will be completed at Screening; All other visits will be a brief physical examination consisting of heart, lung, abdomen and

Confidential Page 89 of 108

targeted for any AEs. All timepoints are relative to the AM dose. Pre-dose exam can occur any time pre-dose on Day 2, 90 minutes post-dose (±30 min), Day 5, 9 and Day 11 pre-dose exam can occur any time pre-AM dose. For male participants, a testicular exam will be performed at the End of Study visit.

Indivior

09 May 2023

- 6: Chemistry and haematology to be collected pre-AM dose (-1hr) on Days 3, 9, and 14. Only liver function tests to be collected pre-AM dose on Days 5 and 11.
- 7: Vital signs will be completed on Day 1 any time pre-dose, 2 hrs post-dose (±30 min), and 4 hrs post-dose (±30 min) on Days 2, 3, 5, 7, 9, 11, 13. All timepoints are relative to the AM dose. Triplicate SBP and DBP assessments will be obtained at least 1 minute apart on pre-dose Day 1 and as needed to assess stopping criteria.

8:12-lead ECG tracing is to be obtained at admission, and on Days 2, 3, 5, 7, 9, 11 and 13 at pre-dose (-1 hr), 2 hrs post-dose (±30 min). All timepoints are relative to the AM dose. Triplicate tracings will be obtained at least 1 minute apart on pre-dose Day 1 and as needed to assess stopping criteria.

13: Baseline assessment to occur at Day -1, all remaining assessments will be 'Since Last Visit' CSSR-S.

Confidential Page 90 of 108

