24 mg/6 mg of buprenorphine/naloxone. If run-in criteria are met, each subject will continue dosing with their stabilized dose of SUBOXONE SL film after the run-in period for required inclinic dosing. Qualifying subjects will continue to Day 1, where SUBOXONE SL film dosing alone continues for 2 more days. On Day 3, subjects will begin receiving doses of both SUBOXONE SL film and INDV-2000 for 7 days. Starting on Day 10, subjects will stop dosing with SUBOXONE SL film and dose with INDV-2000 alone for 4 more days and remain in clinic until completion of assessments on Day 14. Rescue medications to treat opioid withdrawal signs and symptoms will be allowed in the study based on Investigator's medical judgment. After assessments are completed on Day 14, subjects can begin a standard of care treatment for OUD. The EOS visit is scheduled for Day 21. If at any stage of the study a subject discontinues, they will be given options for their continued treatment for OUD by the clinical facility.

A schematic depicting the study design is in Figure 1.

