14.9.1 Treatment-Emergent Adverse Events (TEAEs)

A TEAE is defined as an AE with start date/time at or after dosing with IMP. The number and percentage of subjects reporting TEAEs will be presented for each treatment by MedDRA system organ class (SOC) and preferred term (PT), each in descending order of frequency among all subjects in the given part of the study (then alphabetically in case of ties).

Incidence and number of study drug-related TEAEs, TESAEs, study drug-related TESAEs, TEAEs leading to death, TEAEs leading to IMP discontinuation, and TEAEs leading to IMP interruption will be presented both in an overall summary table and by SOC and PT. Included in the overall summary table will be incidence and number of severe TEAEs and TEAEs with grade 3 or higher toxicity grade (applicable for Parts I and II only). TEAE incidence will also be summarized by maximum severity within SOC and PT. Incidence of TEAEs will be summarized by PT only (not SOC) in descending order of incidence among all subjects (within study part).

In summaries by severity and relationship to study drug, if more than one TEAE is coded to the same PT for the same subject, the subject will be counted only once for that PT using the most severe/most related occurrence. Missing severity, toxicity, and relatedness will be queried until resolution.

Non-TEAEs and, for Part III, run-in AEs in the Run-In Safety Population will be summarized separately.

Separate listings will be presented for TEAEs, TESAEs, TEAEs leading to IMP interruption or discontinuation and TEAEs leading to death.

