14.9.5 Physical Examination

Clinically significant physical examination changes from screening will be reported as AEs; therefore, there will be no separate listings or summaries of physical examination findings.

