22.2 APPENDIX 2 - Schedule of Events Part II

				In	Clinical	Unit (Day	s)			Discharge	0	utpatient	(Days)		Follow-up
Evaluation	Screening Days -28 to -1	-1	1	2	3	4	5	6	7	8	10 (±2)	15 (±2)	22 (±2)	28 (±2)	Day 35/EOS/ET ¹² (± 3 days)
Informed Consent	X														
Inclusion/Exclusion Criteria	X														
Randomization		X													
Admission to Clinical Unit ¹		X													
COVID-19 PCR Test		X													
Discharge from Clinical Unit ²										X					
Demographics (Includes height, weight and BMI)	X														
Medical History	X														
Physical Examination ³	X	X	X	X		X				X	X	X	X	X	X
Urine Drug Screen	X	X													
Alcohol test	X	X													
Serum Pregnancy Test	X														X
Urine Pregnancy Test		X										X		X	
Urinalysis	X	X							X			X		X	X
Clinical Laboratory Assessments (Chemistry and Haematology)	X	X	X ⁴		X ⁴		X ⁴			X ⁴	X^4	X ⁴	X ⁴	X ⁴	X
Serology (HIV, Hepatitis B and C)	X														
Coagulation Panel (PT/INR)	X														
FSH (post-menopausal females only)	X	_													
Vital Signs	X	X	X ⁵	X^5	X^5	X^5			X	X^5	X^5	X ⁵	X ⁵	X^5	X

Page 84 of 108

				In	Clinical	Unit (Day	s)			Discharge	0	utpatient	(Days)		Follow-up
Evaluation	Screening Days -28 to -1	-1	1	2	3	4	5	6	7	8	10 (±2)	15 (±2)	22 (±2)	28 (±2)	Day 35/EOS/ET ¹² (± 3 days)
12-Lead Electrocardiogram	X	X	X ⁶	X ⁶	X ⁶	X ⁶			X ⁶		X^6	X ⁶	X ⁶	X ⁶	X
26-Hour Holter															
Monitoring ⁷															
PK Sampling ⁹			X	X	X	X	X	X	X	X	X	X	X	X	
Drug Administration ¹⁰			X	X	X	X	X	X	X	X	X	X	X	X	
AE Assessment	X	X	X	X	X	X	X	X	X	X	X	X	X	X	X
Prior or Concomitant Medication Assessment	X	X	X	X	X	X	X	X	X	X	X	X	X	X	X
C-SSRS ¹¹	X	X	X			X			X	X	X	X	X	X	X

- 1: Confirm Check-In Criteria (defined in Section 5.4) prior to admission to the unit
- 2: Discharge occurs after completion of assessments.
- 3: A full physical examination will be completed at Screening. All other visits will be a brief physical examination consisting of heart, lung, abdomen and targeted for any AEs. All timepoints are relative to the AM dose. Pre-dose exam can occur any time pre-dose on Day 1, 90 minutes post-Day 1 dose (±30 min), Day 2 24 hr post-Day 1 dose (±2 hr), and Day 4 72 hours post-Day 1 dose (±2 hr). To be performed also on Day 8 before discharge, and Day 10 at 72 hours post-Day 7 dose (±2 hr). On outpatient days, physical exam can occur any time prior to AM dosing. For male participants, a testicular exam will be performed at the Screening and End of Study visits.

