**Figure 1. Study Schematic**

Key features of the study design are described below.

- Part III is an open-label study in OUD treatment-seeking individuals.
- Part III dose determination will follow a blinded review of safety and PK data from Parts I and II.
- The screening period for Part III is up to 35 days. Subjects will receive SUBOXONE SL film during a 6-day, in-clinic run-in period. Qualifying subjects will then be enrolled into the study, consisting of a 14-day in-clinic period followed by an EOS visit on Day 21. Subjects will receive SUBOXONE SL film alone on Days 1 and 2, SUBOXONE SL film and INDV-2000 on Days 3-9, and INDV-2000 alone on Days 10-13. Total study duration per subject, from screening through the EOS visit, will be approximately 56 days.

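### Part III's only timed post-dose physical examination is on Day 2, before INDV-2000 starts; none is timed after an INDV-2000 dose

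*Protocol*

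**What the plan says.** **Treatment by day.** Protocol 4.1 says of the period after run-in: "Qualifying subjects will continue to Day 1, where SUBOXONE SL film dosing alone continues for 2 more days". It continues: "On Day 3, subjects will begin receiving doses of both SUBOXONE SL film and INDV-2000 for 7 days". The SAP agrees (1.2, key design features): "Subjects will receive SUBOXONE SL film alone on Days 1 and 2, SUBOXONE SL film and INDV-2000 on Days 3-9". INDV-2000 then continues alone on Days 10 to 13.

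**Examinations in Part III.** The physical examination row in Protocol 22.3.2 is marked on Days -1, 2, 5, 9, 11, 14 and 21. Footnote 5 ties its timepoints to the morning dose and sets the Day 2 timing: "Pre-dose exam can occur any time pre-dose on Day 2, 90 minutes post-dose (±30 min"). It then gives Days 5, 9 and 11 their own instruction, at any time before the morning dose. Day 14 is the discharge morning and Day 21 the end-of-study visit; neither has a post-dose time.

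**Examinations in Parts I and II.** The Part II footnote (Protocol 22.2, footnote 3) reads: "Pre-dose exam can occur any time pre-dose on Day 1, 90 minutes post-Day 1 dose (±30 min"), followed by checks at 24 and 72 hours. Part I (22.1, footnote 3) has the same pattern. In both parts Day 1 is the first IMP dose.

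**How findings reach the analysis.** Protocol 14.9.5: "Clinically significant physical examination changes from screening will be reported as AEs". The same section plans no separate listing or summary of examination findings. Protocol 14.9.1: "A TEAE is defined as an AE with start date/time at or after dosing with IMP". IMP means INDV-2000 or its placebo (Protocol 9.1), so SUBOXONE alone does not start the treatment-emergent period.

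**The concern.** The Part III primary objective is the safety of INDV-2000, alone and with SUBOXONE, in people with OUD (Protocol 2.1). The primary endpoint consists of treatment-emergent adverse events, and an examination finding reaches that endpoint only by being reported as one.

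The examination best placed to pick up a short-lived sign soon after dosing falls on a day when the investigational drug has not yet been given. Whatever it finds cannot count towards the primary endpoint. The first combined dose, on Day 3, has no scheduled examination before or after it on that day or the next. In Parts I and II the same 90-minute timing is anchored to the first IMP dose, so the Part III placement departs from the protocol's own pattern, and no reason is given.

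**Working it through.** No sample size or error rate is involved. The check sets the schedule rows in Protocol 22.3.2 against each other and against footnote 5.

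**Step 1: rows of the Part III schedule (16 day columns, Day -1 to Day 21)**

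| Row | Days marked |
|---|---|
| SUBOXONE administration | 1 to 9 |
| INDV-2000 administration | 3 to 13 |
| Physical examination | -1, 2, 5, 9, 11, 14, 21 |
| Vital signs; 12-lead ECG | -1, 1, 2, 3, 5, 7, 9, 11, 13, 21 |

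INDV-2000 dosing days: 13 − 3 + 1 = 11.

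**Step 2: timing of each examination**

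| Day | Drug given that day | Examination timing |
|---|---|---|
| -1 | SUBOXONE (run-in) | no post-dose time |
| 2 | SUBOXONE alone | pre-dose, and 90 min (±30) post-dose |
| 5, 9 | SUBOXONE and INDV-2000 | before the morning dose |
| 11 | INDV-2000 alone | before the morning dose |
| 14 | none (last INDV-2000 dose is on Day 13) | discharge day, no post-dose time |
| 21 | none | end of study |

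Footnote 5 is loosely punctuated. Because Days 5, 9 and 11 carry their own pre-dose instruction, the 90-minute time can belong only to Day 2.

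**Step 3: counts**

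- Examinations on INDV-2000 dosing days: 3 (Days 5, 9 and 11), all pre-dose.
- Examinations with a post-dose time on INDV-2000 dosing days: 0 of 11 days.
- First examination after the first INDV-2000 dose: Day 5 morning minus Day 3 morning = 2 × 24 h = about 48 h. Part III dosing frequency is not fixed in the documents. By then a subject has had 2 × 1 = 2 doses if dosed once daily, or 2 × 2 = 4 if twice daily.
- Time from the most recent INDV-2000 dose to a pre-morning examination on Day 5, 9 or 11: about 24 h if once daily, about 12 h if twice daily.

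**Step 4: comparison with Parts I and II**

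| | Parts I and II | Part III |
|---|---|---|
| 90-minute examination | after first IMP dose (Day 1) | Day 2, one day before first IMP dose |
| Next scheduled examination after first IMP dose | 24 h (±2 h), then 72 h (±2 h) | about 48 h (Day 5) |

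The 24- and 72-hour checks in Parts I and II fall around a later morning dose, so they are the same kind of check as Part III's Day 5 examination. Compared like with like around the first IMP dose, the difference is one 90-minute brief examination, plus a next check at about 48 hours instead of 24.

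**Step 5: where a Day 2 finding goes**

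It starts before first IMP, so it is not treatment-emergent. Under Protocol 10.1.1 it is a run-in event. Under SAP 5.5.2 it fits the class of events starting after run-in but before first IMP, summarised for the Run-In Safety Population. Either way it is reported, but outside the primary endpoint.

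**The case against.** The strongest reply is that little depends on this examination.

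- **Day 3 is monitored.** Vital signs are scheduled at 2 and 4 hours post-dose and ECG before and 2 hours after the dose. Chemistry and haematology, PK sampling and adverse event assessment also fall on that day. Subjects live in the unit, and an investigator must be present at in-clinic dosing (Protocol 9.7). Adverse events may be volunteered, solicited or observed (10.1). The missing item is a brief examination of heart, lung and abdomen, targeted to adverse events.
- **Day 2 may be deliberate.** It also carries PK sampling, vital signs, ECG and C-SSRS, which would suit a SUBOXONE-alone reference day.
- **Nothing promises otherwise.** No section commits to a physical examination after an INDV-2000 dose in Part III.

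All of this stands and limits the point. It does not change the zero count or the 48 hours, and no stated purpose explains the Day 2 timing.

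A reader might infer more than the documents support:

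- *That first combined exposure goes unobserved.* It does not. Some rows and footnotes of the schedule are also not visible, so the statement can concern only the physical examination row.
- *That adverse event ascertainment is biased.* No figure in the documents supports a size, or even shows that events would be missed.
- *That a comparison with Parts I and II is spoiled.* The parts are summarised separately (Protocol 14.1) and the Part III analysis is descriptive only (SAP 2). No planned analysis compares examinations across parts.
- *That SUBOXONE is a comparator.* Part III is a single open-label group, with SUBOXONE given before and alongside INDV-2000.
- *That this is a proven drafting slip.* The laboratory row differs from the examination row in one cell only (Day 3 instead of Day 2), which is suggestive. It is not proof, since a SUBOXONE-alone reference remains possible.

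**Conclusion.** The point holds as a limited mismatch between the timing of one assessment and the drug under study. In Part III no scheduled physical examination is timed after an INDV-2000 dose on any of the 11 dosing days. The first after INDV-2000 starts comes about 48 hours after the first dose, and the only 90-minute post-dose examination precedes all IMP exposure. This applies to every one of the up to 16 subjects.

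The conclusion rests on reading footnote 5 so that the 90-minute time belongs to Day 2 alone, and on the visible part of the schedule. It concerns the brief physical examination only and does not threaten the validity of Part III. It is a cheap improvement of minor severity, worth making because examination findings count towards the primary endpoint only as treatment-emergent events.

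**What to change.** In Protocol 22.3.2, reconcile the examination row and footnote 5 with the Day 3 start of INDV-2000, in one of two ways:

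1. **Move it.** Shift the Day 2 mark to Day 3, and have footnote 5 place the examination before, and 90 minutes (±30) after, the first INDV-2000 dose. The footnote should name INDV-2000 as the reference dose, because both drugs are given that morning and footnote 3 puts SUBOXONE second. Examination days become -1, 3, 5, 9, 11, 14 and 21, still seven. Dosing days with a timed post-dose examination go from 0 to 1 of 11, and the first examination after INDV-2000 starts moves from about 48 hours to 90 minutes. The Day 3 pre-dose examination still gives a SUBOXONE-alone reference.
2. **Explain and add.** If Day 2 is meant as a SUBOXONE-alone post-dose reference, say so, and attach the 90-minute time to an INDV-2000 dosing day as well.

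**Cost.** The first option changes one cell and one footnote. Subjects are already in the unit on Day 3, with vital signs and ECG at similar times. It gives up the post-dose look under SUBOXONE alone, which feeds only the summaries of events that are not treatment-emergent. The second option keeps that look at the price of one further timed examination, on an added day unless it is attached to Day 5, 9 or 11. Neither changes a dose, a stopping rule or an analysis.

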22.4 APPENDIX 4 – Liver Safety

The following must occur if a subject meets any of the liver chemistry stopping criteria as outlined in Section 6.5 of the protocol:

- Subject must immediately be withdrawn from treatment. Do not re-challenge with study treatment.
- Notify the Indivior Medical Monitor or specified designee within 24 hours of learning of the abnormality.
- Completed the "Safety Follow-up Procedures" listed below.
- Upon completion of the safety follow-up, the subject must be withdrawn from the study unless further follow-up is required.

Subjects with ALT $\ge 3x$ ULN and bilirubin $\ge 2x$ ULN (>35% direct); or ALT $\ge 3x$ ULN and INR >1.5:

This event is an SAE and must be reported using the SAE Reporting Form (Section 11). Serum bilirubin fractionation should be performed, if testing is available. If fractionation is unavailable, urinary bilirubin is to be measured via dipstick (a measurement of direct bilirubin, which would suggest liver injury).

Make every reasonable attempt to have the subject return to the clinic within 24 hours for repeat liver chemistries, additional testing and close monitoring (with specialist or hepatology consultation recommended).

Monitor the subject twice weekly until liver chemistries (ALT, AST, alkaline phosphatase, bilirubin) resolve, stabilize or return to within baseline values.

Subjects with ALT $\geq 5x$ ULN or ALT $\geq 3x$ ULN who have hepatitis symptoms or rash, cannot be monitored for 4 weeks or have elevations that persist ≥ 4 weeks:

- Make every reasonable attempt to have the subject return to the clinic within 24-72 hours for repeat liver chemistries and additional testing.
- Monitor subject weekly until liver chemistries (ALT, AST, alkaline phosphatase, bilirubin) resolve, stabilize or return to within baseline values.

Subjects with ALT ≥3x ULN and <5x ULN and bilirubin <2x ULN, who do not exhibit hepatitis symptoms or rash:

• Contact the Indivior Medical Monitor within 24 hours of learning of the abnormality to discuss subject safety.

- Subject may continue study treatment, if liver chemistries (ALT, AST, alkaline phosphatase, bilirubin) can be monitored weekly for up to 4 weeks.
- If the subject later meets the liver chemistry stopping criteria (outlined in Section 6.5 of the protocol), immediately withdraw study treatment, perform additional testing and continue safety follow-up until liver chemistries resolve, stabilize or return to baseline values.
- After 4 weeks of monitoring, if ALT <3x ULN and bilirubin <2x ULN, subject must be monitored twice monthly until liver chemistries normalize or return to within baseline values. Additional follow-up procedures for subjects who meet any of the stopping criteria:
- Viral hepatitis serology including:
 - o Hepatitis A Immunoglobulin M (IgM) antibody,
 - HBsAg and Hepatitis B Core Antibody (IgM),
 - o Hepatitis C RNA,
 - o Cytomegalovirus IgM antibody,
 - Epstein-Barr viral capsid antigen IgM antibody (or if unavailable, obtain heterophile antibody or monospot testing), and
 - Hepatitis E IgM antibody.
 - o Blood sample for PK analysis, obtained within 48 hours of last dose.
 - o Serum creatine phosphokinase and lactate dehydrogenase.
 - o Fractionate bilirubin, if total bilirubin $\geq 2x$ ULN.
 - Assess eosinophilia.
 - Record the appearance or worsening of clinical symptoms of hepatitis (fatigue, nausea, vomiting, right upper quadrant pain or tenderness, fever, rash or eosinophilia) as relevant on the AE eCRF.
 - o Record use of concomitant medications, acetaminophen, herbal remedies, other over-the-counter medications or putative hepatotoxins on the Concomitant Medications eCRF.
 - o Record alcohol use in the eCRF.
 - In addition, the following are required for subjects with ALT $\ge 3x$ ULN and bilirubin $\ge 2x$ ULN (<35% direct) but optional for other abnormal liver chemistries:

INDV-2000 Clinical Study Protocol: INDV-2000-102 09 May 2023

Anti-nuclear antibody, anti-smooth muscle antibody, Type 1 anti-liver kidney microsomal antibodies and quantitative total immunoglobulin G (IgG or gamma globulins).

Serum acetaminophen adduct High-Performance Liquid Chromatography (HPLC) assay (quantifies potential acetaminophen contribution to livery injury in subjects with definite or likely acetaminophen use in the preceding week James 2009]).

[figure not shown]
Indivior

[figure not shown]
Liver imaging (ultrasound, MRI, or CT) to evaluate liver disease. Data must be entered into the eCRF, if these tests are performed.

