6.5.1.1 Part I and II - Individual Stopping Criteria

If the following criteria are met at any point during Parts I or II, the affected individual's dosing will be paused to allow unblinded review of affected individuals by the DRSC before continuing dosing. A healthy volunteer will be discontinued if any of the criteria listed below are confirmed:

AEs:

• The healthy volunteer experiences an SAE that is not clearly unrelated to the IMP.

Laboratory Abnormalities:

The healthy volunteer has an abnormality of one or both of the following parameters, whose temporal relationship to the IMP makes causality plausible, confirmed on repeat testing:

- Serum ALT or AST >3 times the ULN
- Total serum bilirubin >2 times the ULN (>35% direct bilirubin).

Vital Signs:

The healthy volunteer fulfils one or both of the following vital sign criteria based on the mean of triplicate measures (≥ 1 minute apart), that will be completed once the first blood pressure reading is outside the accepted range:

- Systolic blood pressure (SBP) <85 or >170 mmHg and/or change from Baseline >30 mmHg sustained for at least 1 hr (measures repeated every 15 min)
- Diastolic blood pressure (DBP) <45 or >105 mmHg and/or change from Baseline >30 mmHg sustained for at least 1 hr (measures repeated every 15 min)

ECG Criteria:

The healthy volunteer fulfils the following ECG criteria based on the mean of triplicate measures (≥ 1 minute apart), that will be completed once the first ECG demonstrates a prolonged interval:

• QTcF ≥500 msec or uncorrected QT interval of >600 msec.

Plasma INDV-2000 Concentrations

Confidential Page 35 of 108

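### Three liver and pause rules in the protocol's safety text do not agree: an unqualified Appendix 4 branch, a study-level rule that pauses only one cohort, and a reversed direct-bilirubin limit

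*Protocol*

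**What the plan says.** **Liver branch.** Protocol Appendix 4 (Section 22.4) opens with "The following must occur if a subject meets any of the liver chemistry stopping criteria as outlined in Section 6.5 of the protocol", and the first action is "Subject must immediately be withdrawn from treatment. Do not re-challenge with study treatment". It then sorts subjects by ALT. The lowest group has ALT of at least 3 but below 5 times ULN, bilirubin below 2 times ULN, and neither hepatitis symptoms nor rash. After contact with the Medical Monitor within 24 hours, the instruction is "Subject may continue study treatment, if liver chemistries (ALT, AST, alkaline phosphatase, bilirubin) can be monitored weekly for up to 4 weeks". That branch mentions the stops only in its next bullet: "If the subject later meets the liver chemistry stopping criteria (outlined in Section 6.5 of the protocol), immediately withdraw study treatment".

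**Stops.** In Parts I and II (6.5.1.1) the liver stop is ALT or AST above 3 times ULN, or total bilirubin above 2 times ULN with more than 35% direct, "whose temporal relationship to the IMP makes causality plausible, confirmed on repeat testing". When a criterion is met, "dosing will be paused to allow unblinded review of affected individuals by the DRSC before continuing dosing", and "A healthy volunteer will be discontinued if any of the criteria listed below are confirmed". In Part III (6.5.1.3) the transaminase limit is above 5 times ULN, or 2-fold above baseline when baseline is at least 1.5 times ULN, also confirmed on repeat and with feasible causality.

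**Pauses.** The cohort criteria for Parts I and II (6.5.1.2) pause the study. The study criteria for all three Parts (6.5.1.4) pause the current cohort.

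**Timing.** Section 4.1 bases Part II escalation on Days 1-7 of the prior cohort(s), and the Part III dose on data that include Part II Cohort 2 Days 1-7. Section 14.11 places the review for Parts I and II after each cohort is complete.

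**Work-up.** Appendix 4 requires the autoantibody, acetaminophen-adduct and imaging tests for ALT at least 3 times ULN with bilirubin at least 2 times ULN and less than 35% direct. It makes them optional for other abnormal liver chemistries.

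**The concern.** A site with a raised ALT in hand is likely to go straight to the matching band in Appendix 4. The band heading is not limited by Part, by AST, by baseline or by Section 6.5 status, so for some subjects it gives the opposite instruction to the appendix's opening rule. Part II volunteers matter most here, because they dose themselves at home from Day 9 to Day 28, apart from clinic days.

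The pause rules look inverted: the narrower trigger has the wider effect. If two groups are on drug when the study-level count is reached, stopping one of them leaves the other exposed to the risk that triggered the rule. The text also does not say which group is the current one.

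The reversed bilirubin limit would make the fuller work-up optional in the cases that the appendix itself calls SAEs.

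**Working it through.** The plan states no figure on this point, so the check compares the rules with one another.

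**1. The Appendix 4 band against the stops** (all values in multiples of ULN; the band is 3 ≤ ALT < 5)

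- Parts I and II: the stop limit is > 3, so the overlap is 3 < ALT < 5. On a 0.1 grid from 3.0 to 4.9, 19 of 20 values exceed the limit. What separates the branch from the stop is confirmation and causality, which the branch heading does not mention.
- Part III, baseline b ≥ 1.5: the limit is k × b, which falls in the band when k × b < 5. If 2-fold above baseline means twice baseline (k = 2), this holds for 1.5 ≤ b < 2.5 (b = 1.5 gives 3.0; 2.0 gives 4.0; 2.4 gives 4.8). If it means three times baseline (k = 3), it holds for 1.5 ≤ b < 5/3 = 1.67, with limits from 4.5. Such baselines can be enrolled, because exclusion 28 removes only ALT or AST ≥ 3.
- Part III, b < 1.5: there is no ALT overlap, and the branch is legitimate.
- AST: the branch sorts on ALT alone, but the stops use ALT or AST. A Part III subject with ALT 4 and AST 6 fits the branch heading and, once confirmed with feasible causality, also meets the stop.

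**2. Study rule against cohort rule** (number of subjects needed)

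| Event | Cohort, 6.5.1.2 | Study, 6.5.1.4 | Split over two Part I/II cohorts that meets only the study rule |
|---|---|---|---|
| Similar severe AE | 3 | 4 | 2+2 |
| Similar SAE | 2 | 2 | 1+1 |
| Liver | 2 (transaminase, bilirubin or both) | 2 (both) | 1+1 |
| QTcF/QT | 2 | 3 | none; 1+1+1 needs three groups |

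Within one Part I/II cohort, reaching the study count always means the cohort count has been reached too, so the study is paused. Part III has no cohort rule, so a cluster there can trigger only 6.5.1.4.

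The individual rules cover part of the gap. In a 1+1 split of SAEs, "The healthy volunteer experiences an SAE that is not clearly unrelated to the IMP" is itself a pause criterion for each volunteer, and the same holds for liver cases. Severe AEs that are not serious are not on that list, so a 2+2 split has no individual rule behind it.

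**3. How long groups could overlap.** Part II dosing ends on Day 28 and the review needs Day 7, so the overlap is at most 28 − 7 = 21 days, less the review time r. The documents do not give r. Assuming r = 3, 7, 14 or 21 days leaves 18, 14, 7 or 0 days. For the two Part II cohorts this holds only on the Section 4.1 reading; under Section 14.11 the overlap is 0.

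Section 14.11 says nothing about Part III. There, INDV-2000 starts on Day 3, after 6 run-in days and 2 further days on SUBOXONE alone. If admission waits for the dose decision, the overlap with Part II Cohort 2 is 21 − 8 − r = 13 − r days: 10 for r = 3, 6 for r = 7, and none from r = 13. If the run-in proceeds during the review, the bound stays at 21 − r. Both assume that a cohort doses on the same dates.

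**4. Direct bilirubin.** Section 6.5 and the appendix's SAE paragraph use > 35% direct. That paragraph also says that direct bilirubin points to liver injury. The extended work-up alone uses < 35%.

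**The case against.** The branch and Section 6.5 can be read in sequence. A first ALT in the band is not yet confirmed, so it does not meet a stop; the branch says what to do meanwhile, and its own next bullet requires withdrawal if a stop is met later. The opening rule is mandatory and takes in AST, the Part III baseline rule and every Part by reference. The Medical Monitor must be contacted, and both the Medical Monitor and the Investigator sit on the DRSC (Section 15.2). All of this stands, and it reduces the first item to a missing qualifier.

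A reader might infer that Appendix 4 permits a subject who already meets a stop to keep dosing. The opening rule forbids it. A reader might also count the dosing days left after a first raised test, or the chance that some volunteer has a raised ALT, as the size of the harm. Neither measures it. Part II liver tests on Days 3, 5, 8, 10, 15, 22 and 28 are nominally at most 7 days apart, and a second raised value supplies the repeat that leads to withdrawal if causality is plausible. The documents give no elevation rate and nothing on how often the text would be misapplied.

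On the pauses, it can be said that Section 4.1 states which data are reviewed, not when the next group starts; that 6.5.1.4 still brings in the DRSC; and that the sponsor may suspend the study at any time (Section 7). These points limit the gap but do not close it. Nothing in Section 4.1 makes Part III wait for Part II Cohort 2 to finish, and a rule that depends on discretion to reach the other group does not do its job.

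On the bilirubin limit, optional tests are still allowed, and the core work-up applies to everyone who meets a stop. That stands.

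**Conclusion.** The three inconsistencies are real but limited.

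- The Appendix 4 branch is a minor drafting conflict. It properly covers elevations that are unconfirmed, causally implausible or otherwise outside Section 6.5, and it should say so.
- The study-level pause is too narrow only when groups are on IMP at the same time. The exposed cases are events split across groups, chiefly 2+2 similar severe non-serious AEs, and clusters in Part III while Part II Cohort 2 is still dosing. If groups run strictly in sequence, there is no harm. A reader might infer that clusters within a cohort go unchecked; in Parts I and II they do not, because 6.5.1.2 pauses the study at equal or lower counts.
- The bilirubin limit is one inequality sign, probably a slip, and affects work-up only.

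The overlap lengths rest on an assumed review time and on common dosing dates. No endpoint, population or analysis changes.

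**What to change.** 1. Appendix 4, heading of the ALT 3 to below 5 times ULN branch: add *and who do not meet a Section 6.5 liver stopping criterion (ALT or AST) for their Part*.
2. Section 6.5.1.4: pause all ongoing IMP dosing in the study pending DRSC review. Leave the study-wide pause in 6.5.1.2 as it is. Align Section 14.11 with Section 4.1 on when the review takes place.
3. Appendix 4, extended work-up: change the limit to more than 35% direct, once the sponsor's clinicians confirm that this was meant.

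The cost is a few words in a protocol amendment, with no statistical cost. The one practical downside is that, if groups do overlap, the second change may briefly pause an unaffected group.
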